These beneficial effects have been recently upheld by the landmark PROSEVA study, a multicenter, prospective, randomized, controlled trial, that randomly assigned 466 patients with severe ARDS to undergo prone-positioning sessions of at least 16 hours or to be left in the supine position. Their results demonstrated a significant improvement in both 28- and 90-day mortality rates: “the 28-day mortality was 16.0% in the prone group and 32.8% in the supine group ($P < 0.001$). The hazard ratio for death with prone positioning was 0.39 (95% confidence interval [CI], 0.25 to 0.63). Unadjusted 90-day mortality was 23.6% in the prone group versus 41.0% in the supine group ($P < 0.001$), with a hazard ratio of 0.44 (95% CI, 0.29 to 0.67)” (14).

Per these positive findings, PP has been consistently shown to be an effective mechanism to increase oxygenation in patients with ARDS when implemented under the following conditions: early enlisting of treatment and its consistent maintenance for at least 16 hours per day, and with concurrent use of lung-protective therapies. Translating these findings towards treatment of COVID-19 positive patients seems promising given the similarity of manifested symptoms and complications.

Study Protocol: Version 7.0 - October 29, 2020

Full Study Title: Pragmatic Trial Exploring Impact of Patient Positioning in the Management of Patients Infected with COVID19: Supine vs. Prone

Primary Investigator: [name], MSc

2. Rationale and Specific Aims

This study aims to determine if provider-recommended guidance on supine vs. prone positioning of COVID-19 patients requiring supplemental oxygen, who have yet to be placed on mechanical ventilation during their hospitalization, improves outcomes in the inpatient setting. This study will be performed as a pragmatic clinical trial.

We have selected an ordinal primary outcome that reflects increased need and provision of oxygen to maintain patient oxygenation. The scale is similar to the World Health Organization Ordinal Outcome Scale (see Exploratory Outcomes) but provides better discrimination and power to measure the effect of supine vs. proning treatment by ranking patients within each modality of support using the FIO₂ he or she receives. This outcome is 1) easy to quantify through documentation of respiratory support modality and the patient's FIO₂, 2) patient centric, and 3) effectively measures requirements for oxygenation support.

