Data capture will be facilitated by the use of the REDCap Clinical Data Interoperability Services (CDIS) tools. Project team members listed as Key Study Personnel with existing electronic health record (EHR) system access rights will make use of REDCap CDIS tools. These tools are designed to enable transfer of relevant study-related data from the Vanderbilt Research Derivative and/or directly from the EHR into REDCap.

Primary Outcome:

The highest level of support on the 5th day after enrollment according to the following scale adjusted for patient status at enrollment according to the same scale and ranked by mean FIO₂ within each category, as appropriate.

- Death
- ECMO
- Mechanical ventilation (ranked by mean FIO₂)
- Non-invasive ventilation such as BiPAP (ranked by mean FIO₂)
- High flow nasal cannula, e.g. Optiflow, Vapotherm or other similar device (titrated by FIO₂%) (ranked by mean FIO₂)
- Standard nasal cannula (titrated by L/min up to 15 L/min) or face mask (ranked by mean FIO₂)
- Room air

Notes:

- The **mean** value of FIO₂ as a weighted average on day 5 is used for outcome assignment ranking.
- FIO₂ on standard nasal cannula or face mask is estimated as 21 + 3 x liters per minute (LPM) O₂ flow.
- Non-rebreather face mask is highest (worst) rank within the standard nasal cannula or face mask category.

Study Protocol: Version 7.0 - October 29, 2020

Full Study Title: Pragmatic Trial Exploring Impact of Patient Positioning in the Management of Patients Infected with COVID19: Supine vs. Prone

Primary Investigator: [name], MSc

- FIO₂ on high flow nasal cannula, e.g. Optiflow, Vapotherm or other similar device is estimated as the %FIO₂ on the machine.
- For patients who are discharged or lost to follow up before day 5, the last documented modality and FIO₂ will be carried forward.

Secondary Outcomes:

For each day, we will record the most intensive oxygen delivery mode and then, for that highest level of oxygen support device, the max FiO₂ while exposed to that device.

3. Inclusion/Exclusion Criteria

Inclusion:

- This study will enroll COVID-19 positive patients admitted to VUMC who require supplemental oxygen, who have yet to be placed on mechanical ventilation during their hospitalization. We will use the hospital's operational status definition to identify COVID-positive case status.

Exclusion:

- Per above, patients admitted on mechanical ventilation will be excluded from enrollment.

4. Enrollment/Randomization

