The scale remains ordinal in nature. We will use the approach of last value carried forward for patients who are not observed for the full five days. Patients discharged home will be at the bottom end of the scale (generally room air) while those who die will be scored the worst possible outcome. Patients discharged to long term care facility or similar will have their oxygen needs at transfer noted as their final requirements. We do not expect many patients to fall into this category since the endpoint is being measured relatively close in time to the intervention (5 days), and transfer is likely to occur after much later in the clinical course.

Study Protocol: Version 7.0 - October 29, 2020

Full Study Title: Pragmatic Trial Exploring Impact of Patient Positioning in the Management of Patients Infected with COVID19: Supine vs. Prone

Primary Investigator: [name], MSc

In the absence of any pre-existing information about our ordinal outcome, and rapidly evolving statistical capabilities to analyze these data being led by our group and others around the world, we describe a traditional analytical approach with associated sample size considerations. We recognize that in the coming weeks new methods will greatly improve the statistical efficiency of these trials and allow us to draw conclusions from fewer patients enrolled. Importantly, evolving approaches will be Bayesian in nature, which allows for early looks at the data so that we can understand the measurement properties of our ordinal scale and the impact of prone positioning and adjust as necessary.

We will use a proportional odds model to compare outcomes between study groups. Because it is possible that oxygen needs at day 5 are influenced by baseline oxygen requirements, we will adjust for baseline. This will answer the question: ‘for two patients who have the same oxygen requirements at baseline, will the patient who is in the prone positioning arm have lower oxygen requirements at day 5 than the person in the alternative arm’. Our final model will also adjust for age, BMI, smoking status, and baseline comorbidities.

Secondary analyses that involve continuous variables will generally use a proportional odds model with death always coded as ‘worst outcome plus one’. This will prevent bias associated with early death in COVID-19, which is known to have a high mortality right among hospitalized patients. For binary outcomes, a logistic model will be used.

Sample size considerations

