The primary endpoint as an ordinal variable that quantifies provision of oxygen as the main measure of clinical status measured on the fifth day of enrollment. The basis of the outcome is the World Health Organization Ordinal Covid-19 Outcome Scale, and this has been combined with data concerning the intensity of oxygen requirements. Patients are first ranked by categories of oxygenation strategies from the least invasive to the most invasive. Then, within rank, they are assigned a score based on the oxygen delivery settings as follows:

- Death
- ECMO
- Mechanical ventilation (ranked by mean FIO₂ for the day)
- Non-invasive ventilation such as BIPAP (ranked by mean FIO₂ for the day)
- High flow nasal cannula (ranked by mean FIO₂ for the day, estimated from the %FIO₂ recorded on the device)
- Standard nasal cannula (ranked by mean FIO₂ for the day, FIO₂ on standard nasal cannula or face mask is estimated as $21 + 3 \times$ liters per minute (LPM) O₂ flow)
- Room air

To minimize missingness on this primary outcome, we use the approach of last value carried forward for patients who are not observed for the full five days. Patients discharged home are at the bottom end of the scale (generally room air) while those who die will be scored the worst possible outcome. Patients discharged to a long-term care facility or similar have their oxygen needs at transfer recorded as their final requirements. Not many patients are expected in this category because the endpoint is being measured relatively close in time to the intervention (5 days), and when transfers occur in this population, they are likely to occur after much later in the clinical course.

Secondary Endpoints:

The secondary endpoint is constructed the same way as the primary endpoint, but measured on each of the first five days of randomization.

Exploratory Endpoints:

A number of exploratory endpoints have been proposed for this trial, and additional outcome may be proposed as understanding of the underlying disease and treatment course evolves. Below, we list the pre specified exploratory outcomes. For newly proposed endpoints, the analytical approaches will generally be similar to those described below.

- Length of Stay
- ICU Length of Stay
- Intubation yes/no

- Ventilator-free days (VFDs) to 28 days, calculated as a backwards count of whole days from day 28 to the last day in receipt of mechanical ventilation.
- Oxygen Levels
 - Maximum FIO2 for each day 1-5 after enrollment

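### The rules for discharge before day 5 do not separate hospice, so a dying patient can be scored on low-flow oxygen or room air and rank above patients on high flow, BiPAP or a ventilator.

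*Protocol*

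**What the plan says.** Protocol section 2 describes the outcome in terms of support: "We have selected an ordinal primary outcome that reflects increased need and provision of oxygen to maintain patient oxygenation". The assessment is "The highest level of support on the 5th day after enrollment according to the following scale". The levels run from death and ECMO through ventilation, non-invasive ventilation, high flow, and nasal cannula or face mask, to room air. Mean FIO₂ ranks patients within the device levels from ventilation to cannula or mask. Death is the only level not defined by oxygen support.

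Three rules cover patients who leave early:

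- **Any discharge or loss before day 5** (protocol section 2, Notes): "For patients who are discharged or lost to follow up before day 5, the last documented modality" and FIO₂ are carried forward.
- **Home** (protocol section 8; SAP Primary Endpoint equivalent): "Patients discharged home will be at the bottom end of the scale (generally room air".
- **Facility** (protocol section 8; SAP Primary Endpoint equivalent): "Patients discharged to long term care facility or similar will have their oxygen needs at transfer noted as their final requirements".

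The SAP adds that "those who die will be scored the worst possible outcome". On eligibility, the one exclusion in protocol section 3 is that "patients admitted on mechanical ventilation will be excluded from enrollment". Neither document mentions hospice, comfort care or withdrawal of support in eligibility, scoring or sensitivity analysis. The one analysis listed under the SAP heading Sensitivity analysis drops the added site.

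**The concern.** Support given tracks severity only while the clinical team is still trying to meet the patient's oxygen needs. Once care becomes palliative the two can separate: the patient is sicker while the device recorded is lighter or absent. The device may be recorded correctly and still say little about the patient's state.

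At stake is the worst end of the scale, where little information is expected. The protocol's assumed day-5 distribution has 1% deaths, or 0.01 × 550 = 5.5 patients. A few patients discharged to hospice could match that number and be counted well away from it. Providers are unblinded (protocol section 5), so decisions on disposition could differ between arms, although nothing in the documents shows that they would.

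**Working it through.** **1. What the rules do to individual patients.**

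| Patient | Score under the written rules |
|---|---|
| Discharged to a hospice facility on day 3 on 3 L/min | Nasal cannula, FIO₂ = 21 + 3 × 3 = 30%; better than anyone on high flow, BiPAP or a ventilator |
| Discharged to home hospice | Bottom end of the scale, generally room air |
| In hospital, oxygen withdrawn before day 5, alive on day 5 | Room air |
| Discharged to hospice, last documented on high flow or non-invasive ventilation | Keeps that level |
| Support withdrawn during day 5 itself | Keeps the highest device of that day |
| Recorded death by day 5 | Worst |

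The first three rows are the gap; the last three limit it. The documents do not say whether a death after discharge but by day 5 would be sought and would replace the carried-forward value. Protocol section 10 offers only follow-up as needed by disposition.

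**2. Inputs.** From protocol section 8, Sample size considerations: death 1%, intubated 5%, high flow/CPAP/BiPAP 14%, supplemental oxygen 30%, in hospital off oxygen 10%, home 40%; target OR 1.6, 80% power, N = 500, planned enrolment 550. Assumed, because not stated: two-sided alpha 0.05, and every hospice or comfort-care count below.

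**3. The plan's own figure.** Whitehead's formula for 1:1 allocation is N = 12(z₁₋α/₂ + z₁₋β)² / [(ln OR)²(1 − Σp̄³)], where p̄ is the mean of the two arms' level probabilities. With six levels and OR 1.6, Σp̄³ = 0.1196, so N = 12 × (1.960 + 0.842)² / (0.2209 × 0.8804) ≈ 485, against the stated 500. Power at 500 is 81.2%. The figure reproduces. The primary scale has no home level, so merging the two off-oxygen groups into room air (50%) gives Σp̄³ = 0.1959 and N ≈ 531. The distribution seen at the interim look is not given. The scoring point does not depend on this figure.

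**4. Where the scores fall.** Cumulating from the worst end: death occupies 0–1%, ventilated 1–6%, high flow/NIV 6–20%, low-flow 20–50%, room air 50–100%. Low-flow is the second-best category but lies on the worse side of the median. Room air ties the patient with the best half.

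**5. Effect on the odds ratio.** Five levels, 275 per arm, OR above 1 favouring proning. Place k assumed patients in a chosen level, spread the other 275 − k over the distribution (shifted by the true OR in the prone arm), and fit the proportional odds model to the expected counts.

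Example, 6 prone versus 1 control, no other effect, low-flow scoring. Control has 274 × (0.01, 0.05, 0.14, 0.30, 0.50) with 1 added to low-flow: 2.74, 13.70, 38.36, 83.20, 137.00. Prone has 269 × the same with 6 added: 2.69, 13.45, 37.66, 86.70, 134.50. The fitted OR is 0.98.

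| Prone vs control | True OR in others | Low-flow | Room air | With death |
|---|---|---|---|---|
| 6 vs 1 | 1.0 | 0.98 | 1.03 | 0.94 |
| 1 vs 6 | 1.0 | 1.02 | 0.97 | 1.07 |
| 3 vs 3 | 1.0 | 1.00 | 1.00 | 1.00 |
| 6 vs 1 | 1.6 | 1.55 | 1.64 | 1.47 |

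The standard error of the log OR is about 0.16. For 6 versus 1, z under no other effect is −0.12, +0.20 and −0.40 (low-flow, room air, with death). At true OR 1.6 it is 2.64, 2.98 and 2.34, all beyond 1.96.

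**The case against.** **The endpoint is meant to measure oxygen support.** Scoring the device actually given follows the protocol's definition, so this is not a contradiction in the plan. That stands. But the SAP presents the score as its main measure of clinical status, and for these patients the score and the status part company.

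**The frequency is unknown and probably small.** This stands. The protocol expects few transfers, although that remark concerns long-term care and does not reach home hospice or comfort care in hospital. Seven patients in 550 is 1.3%, an assumption. If seven such patients fell at random, a split of 6–1 or worse against proning would have probability (7 + 1)/2⁷ = 6%.

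**A reader might infer that an arm with more hospice patients gains on the endpoint.** The figures do not support this in general. With low-flow scoring that arm still does worse (0.98), only by less than if ranked with death (0.94). The direction reverses only with room-air scoring (1.03).

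**Other outcomes would show later harm.** Partly. The SAP has a day-14 scale and a 28-day worst score, both with a death level, as well as intubation and ventilator-free days. They are exploratory and do not repair the day-5 score. The best level of the modified scale is discharge regardless of symptoms or support needs, so hospice is not separated there either.

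**Ranking living patients with death brings in decisions by unblinded providers.** This is a fair cost. It weighs most against using an in-hospital comfort-care order in the primary score, so that step belongs in a sensitivity analysis.

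**Conclusion.** The gap is real, and no other section closes it: followed as written, the rules can rank a patient discharged to hospice, or a comfort-care inpatient off oxygen, above patients receiving full respiratory support. It would be too strong to say that dying patients generally score at the good end. Those last on high flow or non-invasive ventilation stay there, withdrawal on day 5 keeps that day's highest device, and recorded deaths by day 5 score worst.

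The effect is modest. An assumed 6 versus 1 imbalance moves the null OR from 0.94 (ranked with death) to 0.98 (attenuated) or 1.03 (reversed). Bias under the null needs an imbalance between arms. A reader might also infer that the trial's conclusion could turn on this; no example here changes significance. These results rest on the protocol's assumed distribution, five coarse levels, an unadjusted model and invented counts. The point is a cheap improvement to the scoring rules rather than a threat to the trial.

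**What to change.** Before arm-level data are seen, add one sentence to the protocol Notes under Primary Outcome and to the SAP Primary Endpoint: a patient discharged to hospice on or before day 5, identified from the EHR discharge disposition, is ranked with death and not carried forward. Apply it to the daily secondary endpoint from the day of discharge. All other discharges and transfers keep the current rules.

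Add two sensitivity analyses to the SAP:

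- (a) the device-only score, as now written;
- (b) the revised score, with patients changed to comfort-measures-only care by day 5 also ranked with death.

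The cost is a sentence in each document, a short SAP addition, and disposition and comfort-care order dates from the EHR. The trial already draws its data from the EHR, but the documents do not list these as study fields, so their availability should be confirmed. The downside is that a few patients alive at day 5 are ranked with deaths, and that disposition depends on unblinded providers. Analysis (a) shows how much that matters.

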This study will be performed as a pragmatic controlled clinical trial. Patients fitting inclusion criteria who are admitted to the Vanderbilt University Adult Hospital will be enrolled in this study. Individual patient-level quasi-randomization will be employed. Odd-numbered MRNs will be assigned to the prone positioning and even-numbered MRNs will be assigned to the usual care arm. COVID-19 admissions will be reviewed during the daily COVID huddle, and appropriate study team personnel will facilitate protocol execution, working with the local providers/units.

5. Study Procedures

The study procedures in place involve treatment assignment, as well as electronic data capture. Day zero will be defined as the day of enrollment and treatment assignment. Data will originate from the electronic medical record for all patients, as well as from non-invasive patient wearable positioning sensors for a random subset to ensure protocol fidelity. Patients will be assigned to either one of the two comparator arms. Patients and providers will necessarily be unblinded, but outcomes will be analyzed by a blind assessor. Study arm assignment and the corresponding protocol will be discussed at the beginning of each day during the daily COVID-19 huddle. Workflow will include an initial run in period as we expect implementation uptake to take time. Patients enrolled during this ramp-up and optimization period will be allocated to

Study Protocol: Version 7.0 - October 29, 2020

Full Study Title: Pragmatic Trial Exploring Impact of Patient Positioning in the Management of Patients Infected with COVID19: Supine vs. Prone

Primary Investigator: [name], MSc

either the prone or usual care group as appropriate, but their data will not be included in the final analysis.

Comparator Arm A: COVID-positive patients who require supplemental oxygen, but are not yet mechanically ventilated, will be encouraged to lay in a completely prone position for as much time as is tolerable during hospitalization. Guidelines to ensure standardization include the following:

- Instructions to care-giving teams on how to frame the prone positioning ask to patients
- Request that clinical team provide reminders to the patient to prone if they are able (as feasible given workloads)
 - Suggest putting a pillow under pelvis/abdomen and under the lower legs to alleviate lower back strain
 - Suggest listening to podcast, music, or audiobook

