Pragmatic Trial Exploring Impact of Patient Positioning in the Management of Patients Infected with COVID-19: Supine vs. Prone

Statistical Analysis Plan

Version 1.0
9 January 2021

Contents

Introduction.....	2
Population and Design Considerations	2
Interventions	2
Endpoints	3
Primary Endpoint:.....	3
Secondary Endpoints:	3
Safety endpoints:.....	4
Datasets	4
Main Analysis	4
Safety Analysis	4
Other analyses.....	4
Sensitivity analysis.....	4
Statistical Approach	4
Descriptive Analysis	4
Main Analysis	6
Secondary Analysis.....	6
Missingness.....	6
Subgroup analyses and differential treatment effects	7
Summary	7

[name]

9 January 2021
Date

Introduction

This document describes the statistical analysis plan for a pragmatic trial designed to investigate the use of the prone positioning (PP) as compared to supine positioning to increase oxygenation and improve clinical outcomes in patients hospitalized with oxygen support for Covid-19. Prone positioning has long been used to combat hypoxemia in acute respiratory distress syndrome (ARDS). PP has shown to reduce lung over inflation and bolsters alveolar recruitment. PP also promotes uniformity of vertical pleural pressure gradients resulting in more uniform alveolar size. This trial hypothesizes that because PP serves to balance stress and strain within the lungs of COVID-19 positive patients requiring supplemental oxygen, PP will lead to improved outcomes compared to traditional supine positioning. This statistical analysis plan briefly describes the approach to the design and analysis of this study and is intended to provide enough information for an independent statistician to pursue our approach.

Population and Design Considerations

This study enrolls patients hospitalized for Covid-19 who are in receipt of supplemental oxygen but who are not mechanically ventilated. This study is designed as a pragmatic, parallel group, randomized controlled trial comparing clinical status at 5 days post randomization between patients randomized to a proning intervention and patients randomized to usual care. Eligible patients are allocated to study group based on their medical record number. Assignment of MRNs is considered random.

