- Maximum modified WHO ordinal scale score observed during 28 days of hospitalization, the modification is as follows:
 1. Death
 2. Hospitalized on invasive mechanical ventilation or ECMO
 3. Hospitalized on non-invasive ventilation or high flow nasal cannula
 4. Hospitalized on supplemental oxygenation
 5. Hospitalized not on supplemental oxygen
 6. Discharged/not-hospitalized (regardless of symptoms or organ support needs)
- Modified WHO COVID-19 ordinal scale measured at day 14

Safety endpoints:

- Incidence of Complications related to Positioning (e.g. accidental line displacement, vomiting, falls)

Datasets

Main Analysis

The main analysis for this study will be conducted using an intention-to-treat, or as assigned. All participants who met inclusion criteria and were randomized will be included. Participants will be grouped according to the arm to which they were allocated.

Safety Analysis

A safety analysis will be conducted to explore events associated with proning. This analysis will included all participants and events related to proning will be described regardless of study arm.

Other analyses

Neither a per protocol or complete case analysis is expected. A per protocol analyses might be justified if the number of major protocol deviations (including cross overs) exceeds about five in both arms combined.

Sensitivity analysis

This study was originally designed as a single-center pragmatic randomized controlled effectiveness trial. As the Covid-19 case waxed and waned across the country, and as demand for evidence for proning increased, the decision was made to open additional sites. One additional site was opened, which contributed less than 10% of participants to the dataset. We will repeat our main analyses excluded this additional site. If there are considerable differences, then we will report single site data.

Statistical Approach

Descriptive Analysis

Initially, we will describe the study cohort, both overall and grouped by intervention assignment. To characterize the study sample, demographic, clinical, and lab data will be described overall

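### Odd/even MRN allocation can be read before enrolment and nothing checks that every eligible patient entered, so the comparison the SAP calls randomized is open to selection bias at the enrolment step

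*Protocol*

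**What the plan says.** Protocol section 4 (Enrollment/Randomization) sets the rule: "Individual patient-level quasi-randomization will be employed", and then "Odd-numbered MRNs will be assigned to the prone positioning and even-numbered MRNs will be assigned to the usual care arm". On who enters, it says "Patients fitting inclusion criteria who are admitted to the Vanderbilt University Adult Hospital will be enrolled in this study". On the route, "COVID-19 admissions will be reviewed during the daily COVID huddle", with study personnel working alongside local providers and units.

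Protocol section 5 (Study Procedures) adds that the assigned arm is discussed at that huddle, that patients and providers are unblinded while outcomes are analysed by a blinded assessor, that day zero is the day of enrolment, and that run-in patients are left out of the final analysis. The Regulatory Considerations in section 6 seek a waiver of consent.

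The SAP, under Population and Design Considerations, describes the design differently: "This study is designed as a pragmatic, parallel group, randomized controlled trial", and "Eligible patients are allocated to study group based on their medical record number. Assignment of MRNs is considered random". Its main analysis set (Datasets) is as assigned: "All participants who met inclusion criteria and were randomized will be included".

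Neither document describes allocation concealment, a screening log, or a comparison of eligible with enrolled patients by MRN parity.

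**The concern.** Parity is fixed before admission. Anyone who can see the chart knows the arm before judging whether, or when, the patient enters. The SAP's statement that "Assignment of MRNs is considered random" concerns how the numbers are issued. Parity may well be unrelated to prognosis; enrolment given parity need not be.

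Under a parity rule there is no separate act of randomization, so the only entry event the documents show is enrolment. Day zero hangs on the same event. Both who is counted and when the five-day clock starts could therefore depend on the arm. If sicker odd-MRN patients were entered less often or later, the primary odds ratio would favour prone positioning with no true effect; the same in even-MRN patients would do the reverse. Adjustment removes only what the recorded baseline variables capture.

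**Working it through.** **Inputs from the documents.** Day-5 usual-care distribution (protocol section 8): death 1%, intubated 5%, high flow/CPAP/BiPAP 14%, supplemental oxygen 30%, in hospital without oxygen 10%, home 40%. Target OR 1.6, 80% power, N = 500, then 550. Alpha is not stated; two-sided 0.05 is assumed from the 95% intervals. The documents give no rate of missed eligible patients, so every skip rate below is an assumption.

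**1. The plan's own figure.** For a 1:1 proportional odds comparison, N = 12(z₀.₉₇₅ + z₀.₈₀)² / [ln(OR)²(1 − Σp̄³)]. Here 12 × 7.849 = 94.19 and ln(1.6)² = 0.2209.
- Six rows, averaged over arms, Σp̄³ = 0.1196: 94.19 / (0.2209 × 0.8804) = 484.3, so 485.
- Home and no-oxygen rows merged as room air, control arm, Σp³ = 0.1549: 94.19 / (0.2209 × 0.8451) = 504.5, so 505.

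The stated 500 is reproduced, and 500 × 1.10 = 550. Sample size is not at issue.

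**2. Central illustration.** No true effect. The latent outcome is X + U + logistic noise, with X recorded baseline severity and U severity that clinicians see but the model does not. Both are standard normal with coefficient 1, and the outcome is cut to the day-5 shares above. A share of the sickest fifth (by X + U) of odd-MRN patients is not enrolled. The model was fitted to 120,000 simulated patients and standard errors were scaled to N = 550.

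| Sickest fifth skipped | Prone arm lost | Unadjusted OR; type I error | Adjusted for X: OR; type I error |
|---|---|---|---|
| 0 | 0 | 1.01; 5% | 1.01; 5% |
| 25% | 5.2% | 1.10; 9.5% | 1.07; 7% |
| 50% | 9.9% | 1.20; 21% | 1.12; 11% |
| 75% | 15.2% | 1.34; 46% | 1.21; 21% |

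The zero row should be 1.00 and came out at 1.011, which is simulation noise. Dividing it out gives 1.067/1.011 = 1.06, 1.122/1.011 = 1.11 and 1.205/1.011 = 1.19. A larger repeat agreed to within 0.01, with type I errors one to two points lower. Read the table as approximate.

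**3. Upper-end case.** Remove prone-arm patients by their day-5 outcome, with no adjustment and 250 per arm. The three worst rows hold 1 + 5 + 14 = 20%.
- Losing 5% of the arm means losing a quarter of them. The OR at that cut is (20/80)/(15/80) = 1.33; at the home cut it is (40/55)/(40/60) = 1.09. The common OR is 1.15 (1.16 with rows merged) and type I error about 14%.
- Losing 10% means losing half. The cuts give (20/80)/(10/80) = 2.00 and (40/50)/(40/60) = 1.20. The common OR is 1.35 (1.39 merged) and type I error 45–48%.

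**4. Would arm sizes reveal it?** With 15% of one arm lost, 550/(2 − 0.15) = 297 against 253. The 95% binomial range for an even split of 550 is 252–298, so even this loss stays inside it.

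**5. Dilution in an all-eligible cohort.** If a fraction f of odd-MRN eligible patients was never approached and had usual-care outcomes, the prone arm is a mixture. Power = Φ(√[N(1 − Σp̄³)/12] · ln OR − 1.96). At f = 0 and N = 550: 6.352 × 0.470 − 1.96 = 1.026, so 85%.

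| f | OR | Power at 550 |
|---|---|---|
| 5% | 1.56 | 81% |
| 10% | 1.52 | 76% |
| 15% | 1.49 | 71% |
| 20% | 1.45 | 66% |

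Holding the total at 550 slightly overstates the loss, since an all-eligible cohort would be larger than the enrolled one.

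**The case against.** The strongest reply is that the protocol leaves no room for selection. It says eligible patients will be enrolled, gives the huddle no stated discretion to leave anyone out, and seeks a consent waiver, which closes the usual route for differential entry. Under a parity rule, the SAP's analysis set can even be read as every eligible patient. A reader might infer that the analysis set is simply whoever the huddle chose; the documents do not say that. What stands against the reply is that this is intent, and nothing in either document checks it.

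Second, the primary model adjusts for baseline severity and other covariates, and nobody knows a day-5 outcome at enrolment. Both are true. The figures in step 3 therefore assume perfect foresight and no adjustment, and should not be read as expected bias. Step 2 is the fairer guide, and its skip rates, direction and prognostic model are also assumed.

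Third, a reader might infer that an EHR-defined cohort would remove the bias and should replace the primary set. The documents do not support that either. Eligibility depends on needing oxygen, and unblinded providers who can see the MRN decide on oxygen; a query inherits those decisions. Moving day zero would also change the protocol's primary endpoint, and power would fall below 80% if about 10% of odd-MRN eligible patients were never approached.

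**Conclusion.** The exposure is real and limited to the enrolment step. The arm is knowable before entry, no concealment is described, complete enrolment is intended but unverified, and the SAP's label is stronger than the protocol's. There is no evidence in the documents that selection occurred.

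Under the step 2 assumptions the bias after adjustment is modest against a target OR of 1.6: type I error is about 7% or 11% if 5% or 10% of one arm is lost, and reaches about 21% only if 15% is lost. These sizes depend on the assumed skip rates and on recorded and unrecorded severity carrying equal weight. Because arm counts alone would not show the problem, the plan should contain a check that can.

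**What to change.** Keep the parity allocation and the enrolled primary set. In the SAP, before any result by arm is seen:

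- Add a sensitivity analysis of all patients who met the inclusion criteria, identified by EHR query, grouped by MRN parity whether or not they were enrolled, with day 0 at first eligibility.
- Exclude the run-in by a fixed calendar date; neither document gives one. Include the second site only if it can supply the same extract, since the Research Derivative named in protocol section 2 is the lead centre's.
- Report eligible and enrolled counts, and baseline severity, by parity.
- Replace the randomized and considered-random wording with: quasi-randomized by MRN parity, allocation not concealed.
- State that the conclusion will be limited if the two analyses differ.

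The cost is one further EHR query, using tools already in the plan, and a note to the IRB. The sensitivity estimate will be diluted by eligible patients never approached (step 5: OR about 1.56–1.52 and power 81–76% for 5–10%). A shift towards 1 is therefore not by itself proof of selection and must be read beside the counts by parity. The analysis narrows the enrolment route only and does not deal with unblinded decisions on oxygen.
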